	
Cohort 3 may begin dosing at least 24 hours after all participants in Cohort 2 have received their first dose, and available (blinded) safety and tolerability data have been reviewed by the SRC. Based on the available data, a decision will be made to begin dosing of Cohort 3.
 
Participants will be provided with a diary. Starting the day of IMP administration, they will fill in the diary daily for 7 days, recording their temperature, and any solicited local and systemic symptoms of reactogenicity.
 
Capsaicin Challenge
 
A capsaicin-induced increase in DBF model will be used to assess the PDs of the UB-313-mediated immune response. Personnel who will perform these assessments will not be involved in UB-313 safety and tolerability evaluation due to the potential of unblinding. The capsaicin challenge will be conducted at Screening, Baseline before the first dose, and every 4 weeks up to Week 20 and subsequently every 8 weeks until the end of study at Week 44. After Week 16, LSCI assessment may no longer be required once the average capsaicin induced DBF increase within that cohort has returned to baseline (i.e., DBF response ± 2 SD before administration of IMP within a cohort).

Total Expected Number of Participants	Approximately 40 eligible healthy male and female participants (10 per cohort) will be enrolled to receive UB-313 or placebo.
Main Inclusion Criteria	
Full details of inclusion criteria are listed in the protocol. The main inclusion criteria include:
 
• Is a male or female aged 18 to 55 years old, inclusive, at time of informed consent.• Has a body mass index between 18 and 30 kg/m², inclusive at Screening, and with a minimum weight of 50 kg.• Male participants and their partners of childbearing potential must commit to the use of highly effective contraceptives for the study duration and for at least 12 weeks after the last dose. Men must refrain from donating sperm during this same period.• Female participants must be of nonchildbearing potential, or, for women of childbearing potential, must be willing to practice highly effective contraception throughout the duration of the study and for at least 24 weeks following the last dose.

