IMP Injection ¹⁸			X					X								X				
Solicited local and systemic reactions assessment			X					X							X					
Extended unit stay ⁵			X ⁵					X							X					
Diary review ¹⁰			X	X		X		X	X		X				X	X		X		
General Safety Assessments																				
Vital signs (pre- and post-IMP) ^{6,7}	X		X	X		X		X	X		X	X		X	X		X	X	X	X
Height	X																			

Visit Number ¹	Screen ²	V1 ^{2,5}		V1a ⁵	V1b ⁵	V2	V3 ⁵		V3a ⁵	V3b ⁵	V4	V5	V6 ⁵		V6a ⁵	V6b ⁵	V7	V8	V9, V10, V11	V12/ET
Week	Up to 4 wks	W0				W1	W4				W5	W8	W12				W13	W16	W20, W28, W36	W44
Day (Visit Window)	-28 to - 1	D1 (-3D)	D1 --	D2	D3	D8 (±3D)	D29 (-3D)	D29 (±3D)	D30	D31	D36 (±3D)	D57 (±5D)	D85 (-3D)	D85 (±3D)	D86	D87	D92 (±3D)	D113 (±7D)	D141, D197, D253 (±14D)	D309 (±14D)
Visit Type	SRN	Pre IMP	IMP	CRU	TC	CRU	Pre IMP	IMP	CRU	TC	CRU	CRU	Pre IMP	IMP	CRU	TC	CRU	EoT CRU	CRU	EoS/ET CRU
Weight	X		X					X						X				X	X	X
Physical exam ^{4,8}	X		X					X						X				X		X
Neurological exam ^{4,8}	X		X					X						X				X		X
TriPLICATE ECGs ⁴	X		X			X		X			X			X				X	X	X
MRI ¹⁷	X																			
Laboratory Assessments ^{4,9}																				
HIV, HCV, HBV	X																			
Coagulation	X																			
Clinical chemistry ⁴	X	X				X	X				X	X	X					X	X	X
Hematology ⁴	X	X				X	X				X	X	X					X	X	X
Urinalysis ⁴	X	X				X						X						X		X
Urine drug screen ⁴	X	X				X						X								
Pre-IMP alcohol breath test ⁴	X		X					X									X			
Pre-IMP pregnancy test ^{4,11}	X		X					X									X			
FSH ¹¹	X																			
Inflammatory markers ^{4,12}	X	X				X						X						X		X
Cytokine panel (pre- and post- IMP) ¹³		X	X			X	X					X	X							
Pharmacodynamic Assessments ⁴																				
Serum antibodies ^{4,14}		X				X	X				X	X	X					X	X	X
Serum CGRP ⁴		X				X	X				X	X	X					X	X	X

Visit Number ¹	Screen ²	V1 ^{2,5}		V1a ⁵	V1b ⁵	V2	V3 ⁵		V3a ⁵	V3b ⁵	V4	V5	V6 ⁵		V6a ⁵	V6b ⁵	V7	V8	V9, V10, V11	V12/ET
Week	Up to 4 wks	W0				W1	W4				W5	W8	W12				W13	W16	W20, W28, W36	W44
Day (Visit Window)	-28 to -1	D1 (-3D)	D1 --	D2	D3	D8 ($\pm 3D$)	D29 (-3D)	D29 ($\pm 3D$)	D30	D31	D36 ($\pm 3D$)	D57 ($\pm 5D$)	D85 (-3D)	D85 ($\pm 3D$)	D86	D87	D92 ($\pm 3D$)	D113 ($\pm 7D$)	D141, D197, D253 ($\pm 14D$)	D309 ($\pm 14D$)
Visit Type	SRN	Pre IMP	IMP	CRU	TC	CRU	Pre IMP	IMP	CRU	TC	CRU	CRU	Pre IMP	IMP	CRU	TC	CRU	EoT CRU	CRU	EoS/ET CRU
PBMC for ELISpot ⁴		X																X		
Blood collection for research sample ^{4,15}		X				X	X				X	X	X				X	X	X	X
HLA typing (optional)																			X ¹⁹	X ¹⁹

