**Figure 1 Study Design Schematic**

\*No more than 4 participants will be dosed in a 24-hour period.

\*No more than 4 participants will be dosed in a 24-hour period.

Abbreviations: C (capsaicin Challenge); EoS (End of Study); EoT (End of Treatment); M (month); SCR (Screening Period); h (hour); Wk (week).

SRC (Safety Review Committee) is responsible for the safety review and dose escalation decision. At the end of Week 16, an EoT analysis will be performed for each cohort, unblinded by treatment cohort and pooled by dose on all safety, tolerability, immunogenicity and DBF data. At the end of the treatment analysis, study team members who are responsible for the conduct and data management of the study, and participants will remain blinded to the subject level treatment assignment. If there are no safety concerns, the study will continue until all participants complete Week 44 (End of Study [EoS]) visit. An unblinded statistics team from an external CRO (AvanSight) will perform the EOT and EOS analyses.

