### **4.0 General Consideration**

All analyses will be conducted using observed data only and no missing data will be imputed.

In general, the baseline value is defined as the last available value before the first injection of study dose.

All analysis and summary will be performed by dose group, defined as below:

- 100/100/100 $\mu$ g (8 active participants in cohort 1)
- 300/100/100 $\mu$ g (8 active participants in cohort 2)

- 300/300/300 $\mu$ g (8 active participants in cohort 3)
- 600/100/100 $\mu$ g (8 active participants in cohort 4)
- Placebo (8 participants from all cohorts)

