### 5.1.1.3      **Seroconversion and Responder Rate (Exploratory)**

Additional exploratory endpoints are seroconversion status and sero responder status for each participant.

Seroconversion is defined as the ratio (i.e., geometric mean fold change) of post baseline titer over baseline titer  $\geq X$  (e.g., X=1, 2, 3, 4).

Seroconversion rates will be calculated for all postbaseline visits along with 95% CIs based on Binomial distribution. In addition, the difference in the response rates between UB-313 and the placebo group (UB-313 – placebo) will be calculated, and the 95% CIs based on Fisher's Exact test will be displayed.

To define the threshold of response, mean and standard deviation of titer values will be calculated using the assessments below.

- Titer values at baseline from all participants
- and
- Titer values at all postbaseline visits up to Week 16 from placebo participants.

The mean plus two standard deviations (mean+2SD) will be used as the threshold of response. Responders will be defined as the participants with titer value greater than or equal to response threshold for each visit including baseline and postbaseline visits.

Responder analysis will be done similarly to seroconversion rates.

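### The antibody-responder rule (titer at or above mean+2SD, no floor) would score every participant a responder if all reference titers sit at one undetectable value: a minor edge case in an exploratory endpoint

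*SAP*

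**What the plan says.** SAP 5.1.1.3 (Seroconversion and Responder Rate, labelled exploratory) builds the threshold from two sets of values expected to show no response: "Titer values at baseline from all participants", together with "Titer values at all postbaseline visits up to Week 16 from placebo participants". It continues: "The mean plus two standard deviations (mean+2SD) will be used as the threshold of response". The classification rule is: "Responders will be defined as the participants with titer value greater than or equal to response threshold for each visit including baseline and postbaseline visits". The resulting rates are then handled like seroconversion rates, with a binomial interval per group and a UB-313 minus placebo difference with its own interval.

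Three other places bear on the point:

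- SAP 4.0 says that observed data only are used and missing data are not imputed. It does not say how a titer below detection is recorded.
- SAP 5.1 allows log transformation if the distribution looks log-normal.
- The text beside Figure 1 in SAP 2.2 describes the Week 16 readout: "At the end of Week 16, an EoT analysis will be performed for each cohort, unblinded by treatment cohort and pooled by dose". It does not say whether the response threshold is recalculated for each cohort's readout.

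**The concern.** A mean+2SD cut-off works when the reference values vary. Here they come from healthy people before any injection and from saline placebo recipients, so a clean assay could report all of them as undetectable with the same number. The spread is then zero, the threshold collapses onto the undetectable value, and the inclusive inequality turns every undetectable titer into a response. The rule would fail when the assay background is cleanest.

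The responder table would then carry no information. A group in which all 8 active participants truly responded would show the same rate as placebo. The rule would have to be changed after the data had been seen, and SAP 2.2 assigns the EoT and EoS analyses to an unblinded statistics team.

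The weakness does not depend on which reference values are chosen, since a baseline-only set would behave the same way. It is also separate from the example fold-change cut-off of X=1 in the same section.

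**Working it through.** The plan states no threshold value or responder rate, so there is no figure of its own to reproduce. The rule can be applied directly.

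**Inputs**

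- Participants: the protocol synopsis says "Approximately 40 eligible healthy male and female participants (10 per cohort) will be enrolled to receive UB-313 or placebo". SAP 4.0 gives 8 active participants per dose group and 8 placebo participants in total.
- Antibody samples after baseline up to Week 16, from the serum-antibody row of Protocol Table 1: Weeks 1, 4, 5, 8, 12 and 16, so 6.
- Reference set if complete: 40 baselines + 8 × 6 placebo values = 88.
- Not in the documents, so assumed: the background detection rate, and that undetectable samples share one numeric value c, the lowest reportable.

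**Step 1. All reference values equal c.** Mean = c, SD = 0, threshold T = c + 2 × 0 = c. Since c ≥ c, all 88 reference values count as responses. No reportable titer is below c, so all 40 participants respond at every visit. Each group shows 8/8 (exact 95% lower limit 0.025^(1/8) = 63.1%), and every difference from placebo is 0. Logs do not help, because a constant stays constant. Checks with c = 1, 10, 50 and 100, raw and log10, all gave 88/88.

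**Step 2. One value above the floor.** If any reference value exceeds c, the mean exceeds c. Then T ≥ mean > c, so no floor-level titer can be a response. Take one of the 88 values at twice the floor, in units of c:

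- Mean = 1 + 1/88 = 1.0114
- SD = 1/√88 = 0.1066
- T = 1.0114 + 2 × 0.1066 = 1.22

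Reference responders fall from 88 to 1, the raised value itself. With one value ten times the floor, T = 1 + 9/88 + 18/√88 = 3.02 and again only that value responds. The failure therefore needs SD to be exactly 0.

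**Step 3. Probability that SD = 0, under assumed backgrounds.** Let p be the chance that a value is undetectable. If all 88 values are independent, the probability is p^88. If values are fully correlated within person, it is p^40.

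| p | p^88 | p^40 |
|---|---|---|
| 0.95 | 1% | 13% |
| 0.98 | 17% | 45% |
| 0.99 | 41% | 67% |
| 0.999 | 92% | 96% |

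A second model assumes that a fraction q of unexposed people have background reactivity, detectable at half of their visits. Each of the 32 active participants contributes one baseline and each of the 8 placebo participants contributes 7 samples, so

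P(SD = 0) = (1 − q/2)^32 × (1 − q(1 − 0.5^7))^8.

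If the threshold came from one cohort alone, the reference set would be 10 + 2 × 6 = 22 values and the exponents would be 8 and 2.

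| q | All 40 participants | One cohort only |
|---|---|---|
| 0 | 100% | 100% |
| 1% | 79% | 94% |
| 2% | 62% | 89% |
| 5% | 30% | 74% |
| 10% | 8% | 54% |

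These are probabilities that the rule degenerates, not expected responder rates in a given trial.

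**Step 4. Effect of a strict inequality when SD = 0.** Reference responders change from 88/88 to 0/88. For a group in which all 8 active participants have detectable titers, the comparison changes from 8/8 vs 8/8 (difference 0, Fisher p = 1.0) to 8/8 vs 0/8 (difference 100 points, Fisher p = 0.00016).

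**The case against.** The strongest objection is that the trigger is assumed. It needs every reference titer to be identical, undetectable samples to be stored as one number, and that number to be the lowest reportable. No supplied text says so. What indirect evidence there is points the other way: the SAP uses baseline titer as an ANCOVA covariate (5.1.1.1 and 5.1.1.4), added AUC above baseline to adjust for baseline (7.0), and contemplates log-normal titers (5.1). All of this suggests that the authors expected baselines to vary. It stands as a reason to doubt the likelihood. It does not supply a rule for the case where they do not vary.

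A second objection is that nobody would be misled. A table showing 100% responders pre-dose and on placebo would be conspicuous, and titers are also summarized at every visit. This stands too. A reader might infer that a fully effective regimen would be published as no better than placebo. The documents do not support that, because the rule is applied at baseline as well and the failure would be seen. The realistic harm is an uninformative table and a repair made after the results are known.

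A reader might also infer from the probabilities above that the rule inflates responder rates in general. It does not: step 2 shows that floor-level titers stop counting as soon as one reference value is raised. Nor do the documents say that a single-cohort threshold will be used. SAP 5.1.1.3 refers to all participants, so the one-cohort column holds on one reading only.

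Finally, a strict inequality alone cures the arithmetic, and requiring more may look like preference. That is largely right; the reason for the second condition is given with the fix.

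**Conclusion.** The point holds as a conditional edge case of minor severity. As written, the rule gives 100% responders in all five groups at every visit, and a difference of 0 from placebo, if and only if all reference titers share the lowest reportable value. Nothing in the supplied text prevents this. How likely it is cannot be determined from the documents. Under the assumed backgrounds for the full reference set it ranges from 1% to 96% in the first table, and from 8% at q = 10% to 79% at q = 1% in the second.

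Only the exploratory antibody-responder analysis is affected. The primary ANCOVA of change in titer (SAP 5.1.1.1) does not use the threshold. One reservation remains: only the protocol synopsis and schedule were available, so an assay rule elsewhere in the protocol or in laboratory documentation cannot be excluded.

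**What to change.** In SAP 5.1.1.3, define a responder as a participant whose titer is strictly greater than the mean+2SD threshold and also above the value assigned to undetectable titers (or the assay's lower limit, if the assay documentation gives one). State that assigned value, and apply the same definition to the EoT and EoS analyses. The strict inequality removes the degenerate case. The second condition makes it explicit that an undetectable titer is never a response, and protects against rounding in a computed mean of identical logged values.

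The cost is one sentence in the SAP and one line of code, with no new data. The small downside is that a titer exactly at the cut-off no longer counts as a response.

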### 5.1.1.4      **Cumulative AUC for Serum anti-CGRP Antibody Titer and Cmax (Exploratory)**

Cumulative AUC is defined as the area under the curve from Day 1 to each scheduled visit. AUC will be calculated by the sum of individual trapezoid area under the curve of level of antibodies.

AUC from baseline to each postbaseline visit will be calculated. AUC above baseline for each postbaseline will also be calculated (i.e., derive AUC using each postbaseline value change from baseline). In the case of early dropout, the AUC will be calculated up to the last visit with titer values. AUC will not be calculated for the visits after dropout.

$C_{max}$  is the highest observed value up to end of study (EoS).  $C_{max}$  change from baseline will be calculated as  $C_{max} - \text{baseline value}$ .

ANCOVA model will include dependent variable of cumulative AUC and AUC above baseline, with factor of dose group, and baseline titer as covariate.  $C_{max}$  and  $C_{max}$  change from baseline will be analyzed similarly.

#### **5.1.1.5 Quantitative anti-CGRP Antibody Titers (Exploratory)**

Quantitive anti-CGRP antibody titers will be summarized.

#### **5.1.2 Pharmacodynamics (PD) Analyses**

##### **5.1.2.1 Capsaicin Induced Dermal Blood Flow (Secondary Endpoint and Analysis)**

###### Capsaicin-induced increase in DBF (CIDBF)

The pharmacodynamics (PD) endpoint is the inhibition of capsaicin-induced increase in DBF (CIDBF). The DBF at each timepoint at each visit will be calculated as the average of two capsaicin-induced locations.

The DBF will be summarized for each timepoint (i.e., 0, 15, 30, 45, and 60 minutes) at each visit (i.e., Day 1, Day 29, Day 57, Day 85, Day 113, and Day 141, Day 197, Day 253, Day 309 as applicable).

###### Change and Percent Change from pre capsaicin in CIDBF

For each post capsaicin time point at each visit, change and percent change from pre capsaicin will be calculated. For example, change at 30 minutes post capsaicin on Day 29 from pre capsaicin is calculated as the DBF at 30 minutes post capsaicin on Day 29 minus the DBF at 0-minute pre capsaicin on Day 29. Percent change will be calculated similarly.

Summary will be presented. Between dose group comparison will be done. ANCOVA model will include dependent variable of change (or percent change) from pre capsaicin in CIDBF, with factor of dose group, and DBF at 0-minute pre capsaicin as covariate.

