#### Change and Percent Change from Baseline (Day 1 prior to study IMP) in CIDBF

For 30 minutes and 45 minutes post capsaicin at each visit, change and percent change from baseline (Day 1 prior to study IMP) will be calculated. For example, change from baseline at 30 minutes post capsaicin on Day 29 is calculated as the DBF at 30 minutes post capsaicin on Day 29 minus the DBF at 30 minutes post capsaicin on Day 1 prior to study IMP. Percent change will be calculated similarly.

Summary will be presented. Between dose group comparison will be done. ANCOVA model will include dependent variable of change (or percent change) from baseline in CIDBF, with factor of dose group, and DBF at baseline (Day 1 prior to study IMP) as covariate.

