#### **5.1.2.3 CIDBF AUC (Exploratory)**

CIDBF AUC (0-60min) and change from baseline (Day 1 prior to study IMP) will be summarized by dose group for each visit. Between dose group comparison will be done. ANCOVA model will include dependent variable of AUC, with factor of dose group, and baseline AUC as covariate.

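### The ANCOVA of the capsaicin-induced increase (SAP 5.1.2.1) appears to adjust for resting flow measured after dosing; if UB-313 shifts resting flow, the estimated inhibition can be too large or too small, by an amount the documents do not let us size

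*SAP*

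**What the plan says.** SAP 5.1.2.1 sets the pharmacodynamic (secondary) endpoint as inhibition of the rise in DBF that capsaicin produces. The subsection on change from pre capsaicin calculates that rise within a visit: its example takes the 30-minute value on Day 29 "minus the DBF at 0-minute pre capsaicin on Day 29". It then states: "ANCOVA model will include dependent variable of change (or percent change) from pre capsaicin in CIDBF", and completes the model "with factor of dose group, and DBF at 0-minute pre capsaicin as covariate". There is no other covariate.

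The neighbouring models are worded differently. The change-from-baseline subsection adjusts for "DBF at baseline (Day 1 prior to study IMP) as covariate". SAP 5.1.2.3 states: "ANCOVA model will include dependent variable of AUC, with factor of dose group, and baseline AUC as covariate". SAP 4.0 says that "the baseline value is defined as the last available value before the first injection of study dose", and the word baseline is not applied to the covariate at issue.

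A pre-dose challenge exists. The protocol synopsis (Capsaicin Challenge) schedules one before the first dose, and SAP 5.1.2.1 lists Day 1 among the visits at which DBF is summarised at 0, 15, 30, 45 and 60 minutes.

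**The concern.** A covariate in a randomised comparison should be fixed before treatment starts. On the natural reading this one is not. Injections are given at Weeks 0, 4 and 12, and on injection days the challenge comes before the injection (protocol Table 1, note 4). The 0-minute value therefore follows one injection on Day 29, two on Days 57 and 85, and three from Day 113 on.

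If a regimen changes resting flow, part of its effect is conditioned on, and the group coefficient no longer estimates the effect on the increase. This matters because it is the only model in 5.1.2.1 whose outcome is the within-visit increase, which is the endpoint as defined. The change-from-baseline model does hold a Day 1 value, but its worked example uses DBF itself at 30 minutes, not the increase over that visit's resting value. The AUC model is exploratory.

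**Working it through.** The documents state no SD, effect size or power for DBF, so there is no planned figure to reproduce. The check is on wording, algebra and simulation.

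**1. Which visit.** The covariate sentence reuses the term that the preceding example applies to the same-visit value. Where the SAP means a pre-dose value, in the two neighbouring models, it says so. The same-visit reading is therefore the natural one, but it is an inference.

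**2. Algebra (absolute change).** Let DBF_0 and DBF_t be the same-visit values before and after capsaicin, and C = DBF_t - DBF_0. The model is

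C = a + b x group + c x DBF_0.

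Adding DBF_0 to both sides gives

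DBF_t = a + b x group + (c + 1) x DBF_0.

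The coefficient b is the same in both. With s = c + 1 (the within-group slope of DBF_t on DBF_0), E_t the effect on DBF_t and delta the effect on DBF_0:

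- the model estimates b = E_t - s x delta;
- the effect on the increase is E_t - delta;
- the difference is (1 - s) x delta.

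It is zero when delta = 0 or s = 1. For percent change, DBF_0 is also the denominator of the outcome, so this linear formula is not exact there.

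**3. Illustration.** All values are assumed: resting flow 100, increase 150, true inhibition 20%, so the effect on the increase is -0.20 x 150 = -30. The model then gives -30 + (1 - s) x delta.

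| s | delta = -10 | delta = -20 |
|---|---|---|
| 0.3 | -37 (overstated 7/30 = 23%) | -44 (overstated 14/30 = 47%) |
| 0.5 | -35 (overstated 5/30 = 17%) | -40 (overstated 10/30 = 33%) |
| 1.0 | -30 (none) | -30 (none) |
| 1.5 | -25 (understated 5/30 = 17%) | -20 (understated 10/30 = 33%) |

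**4. Simulation.** Settings: 8 against 8, 20,000 runs, no true effect on the increase, units of the resting SD. Here k is the SD of DBF_t over the SD of DBF_0, r is their correlation, and s = r x k. The Day 1 increase is assumed to correlate 0.6 with the later increase.

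| delta | k | r | s | (1 - s) x delta | Bias, SAP model | Bias, Day 1 increase as covariate |
|---|---|---|---|---|---|---|
| 0 | 2 | 0.5 | 1.0 | 0 | -0.006 | -0.001 |
| -0.5 | 1 | 0.5 | 0.5 | -0.25 | -0.249 | 0.002 |
| -0.5 | 2 | 0.2 | 0.4 | -0.30 | -0.292 | -0.009 |
| -0.5 | 3 | 0.8 | 2.4 | +0.70 | +0.701 | 0.005 |
| -1 | 3 | 0.8 | 2.4 | +1.40 | +1.402 | 0.012 |

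The formula holds, the sign depends on s, and the Day 1 covariate removes the bias.

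**5. Precision.** Let q be the correlation of the Day 1 increase with the later increase. In units of resting variance, the residual variance is k^2 x (1 - r^2) for the SAP model and (1 + k^2 - 2rk) x (1 - q^2) with the Day 1 increase alone.

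- k = 1, r = 0.3, q = 0.5: 0.91 against 1.40 x 0.75 = 1.05. The SE ratio is sqrt(1.05/0.91) = 1.07, a rise of about 7%.
- k = 1, r = 0.5, q = 0.5: 0.75 against 1.00 x 0.75 = 0.75, no change.
- k = 2, r = 0.5, q = 0.6: 3.00 against 3.00 x 0.64 = 1.92. The ratio is 0.80, matching the simulated SEs of 0.90 and 0.72. Here s = 1, so the same-visit covariate explains none of the variation in the increase.

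Adding the Day 1 0-minute DBF may recover some precision; that was not calculated.

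**The case against.** The strongest reply has four parts.

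- **The visit is inferred.** The SAP does not say which visit supplies the 0-minute value. This stands. If Day 1 was meant, the model is sound in this respect, but the sentence still has to say so.
- **No effect on resting flow is shown.** The documents treat capsaicin-induced flow as the marker of target engagement; they say nothing of UB-313 changing resting flow. This stands too. A reader might infer that the planned comparison is biased as written, and the documents do not support that. They also give no ground for assuming that resting flow is unaffected.
- **It may be a choice of estimand.** Comparing evoked flow at a given same-visit resting flow is a recognisable target. But the endpoint is inhibition of the increase, and the SAP does not define or defend a conditional version. This supports keeping the model as a sensitivity analysis, not as the only model of the increase.
- **Much is already visible.** DBF at 0 minutes is summarised by group and visit, as is vehicle-site DBF, and the increase is also summarised without adjustment. A shift in resting flow could be seen there. These summaries do not correct the ANCOVA estimate.

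A reader might also infer that omitting the Day 1 increase necessarily wastes precision in groups of 8. That does not follow. The SAP model already has a covariate, and replacing it can lower the SE, leave it unchanged or raise it modestly.

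**Conclusion.** The point holds in conditional form. On the natural reading, the one model of the within-visit increase adjusts for a variable measured after dosing, and its group effect departs from the effect on the increase by (1 - s) x delta. Neither quantity is in the documents, so the size and direction are unknown; the percentages above show what assumed values would do and are not estimates for this trial. The case for change rests on removing a possible bias, not on a gain in precision.

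The weight is moderate. This is a secondary comparison in a first-in-human study with no power basis for its sample size, and the safety and antibody-titer analyses are untouched. It should be corrected because the remedy is cheap and uses data already scheduled.

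**What to change.** Amend the model sentence in the change-from-pre-capsaicin subsection of SAP 5.1.2.1:

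- Use the same-visit 0-minute DBF only to calculate the increase.
- For each visit from Day 29 on, adjust for two values from Day 1 before IMP: the increase at the same post-capsaicin minute and the 0-minute DBF. Name Day 1 in the text. For the percent-change version, use the Day 1 percent increase in the same way.
- Compare same-visit 0-minute DBF between dose groups as a supporting result, beyond the descriptive summary already planned.
- If wanted, keep the same-visit-adjusted model as a labelled sensitivity analysis.

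The cost is a short SAP edit and one extra model degree of freedom. If all 40 participants (4 x 8 + 8) are analysed in one five-group model, residual degrees of freedom go from 40 - 5 - 1 = 34 to 40 - 5 - 2 = 33; in a pairwise 8 against 8 model they go from 16 - 2 - 1 = 13 to 16 - 2 - 2 = 12. A small loss of precision is possible. No new data are needed.
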